Finally, rectal contraction contributes to the desire to defecate. There is limited evidence, more in adolescents than in adults, that chronic constipation is associated with increased rectal compliance. Increased rectal compliance is associated with rectal hyposensitivity. In children and adolescents, increased rectal compliance is associated with severe symptoms but does not predict treatment failure. However, it is unclear if increased rectal compliance causes or is consequent to chronic constipation or if increased rectal compliance reflects reduced rectal contractile response to distention. We now propose to explore this question by using approaches that we have extensively utilized to evaluate rectal pressure-volume relationships in fecal incontinence i.e., distention with a barostat and separately with sinusoidal oscillation.

Psychological factors such as stress or depression are known to influence the natural history of chronic gastrointestinal illnesses such as inflammatory bowel disease (IBD) [15] and irritable bowel syndrome (IBS) [16] via the gut-brain axis. These conditions, and also constipation are also associated with dysbiosis. [17] Furthermore, the gut microbiota-brain axis appears to be bidirectional.[18] It is thus important to also evaluate the gut microbial profile in patients and controls to identify potential interactions between gut microbiota and

the response to stress, in health and in constipation. We propose to assess this using 16s rRNA analysis of stool samples.

This study will evaluate the following specific aims in healthy subjects and in patients with defecatory disorders:

- 1) To assess the effects of a highly-selective  $\alpha_{1A}$  receptor antagonist alfuzosin on anal resting pressure, squeeze increment, and rectoanal gradient during simulated evacuation. Our hypothesis is that  $\alpha_1$  receptors contribute to anal resting pressure but not the squeeze pressure increment in healthy people and defecatory disorders.
- 2) To study the effects of mental stress on anal resting and squeeze pressures via  $\alpha_1$  adrenoreceptors. Our hypothesis is that mental stress will increase anal resting but not squeeze pressure via  $\alpha_1$  adrenoreceptors in healthy people and defecatory disorders.

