- 3) To evaluate the effects of active mental relaxation on anal resting and squeeze pressures. Our hypotheses is that mental relaxation will reduce anal resting pressure via  $\alpha_1$  adrenoreceptors; hence the  $\alpha_1$  adrenoreceptor antagonist will attenuate the reduction in anal resting pressure resulting from mental relaxation in healthy people and defecatory disorders.
- 4) To compare rectal compliance and the response to sinusoidal oscillation. Our hypotheses are that rectal compliance is higher and the contractile response to sinusoidal oscillation is lower in defecatory disorders than in healthy people.
- 5) To explore the effects alfuzosin on bowel symptoms in patients with chronic constipation. Our hypotheses are that alfuzosin will improve bowel symptoms in chronic constipation.

**6) To evaluate the role of microbiota in the relationship between stress/relaxation and defecatory mechanisms. Our hypothesis is that the susceptibility to stress is associated with differences in fecal microbiota. B. Research Design and Methods**

This study comprises 2 parts. Part A will compare the effects of oral alfuzosin (IR 2.5 mg) and placebo on anorectal functions on 1 day in all subjects (controls and patients). Part B will compare the effects of oral alfuzosin ( 10 mg ER) and placebo on bowel habits in constipated patients (but not in healthy subjects). 36 healthy women and 36 women with defecatory disorders will be enrolled in this study. This protocol is limited to women only because the vast majority of patients with constipation and defecatory disorders in our practice are women.

1. Human subjects.

- a) Inclusion Criteria for Controls (Part A only)
  - i. Healthy women volunteers aged 18-80 years
  - ii. Able to provide written informed consent before participating in the study

- iii. Able to communicate adequately with the investigator and to comply with the requirements for the entire study.

b) Inclusion Criteria for Patients (women aged 18-80 years) (Parts A and B)

- i. Constipation. Women with chronic constipation for 1 year with any 2 or more of the following symptoms for 3 months or longer, i.e. <3 bowel motions/week, straining  $\geq 25\%$  of time, hard or lumpy stools  $\geq 25\%$  of time, incomplete evacuation  $\geq \square 25\%$  of time, feeling of anorectal blockage  $\geq 25\%$  of time.
- ii. Able to provide written informed consent before participating in the study

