**THE REST OF THIS PAGE IS INTENTIONALLY BLANK**

**Table 1. Schedule for Study Assessments and Monitoring**

[figure not shown]
	Screening	Acute Study	Bowel Symptoms (Alfuzosin – ER 10 mg)			
	Days –30 to 1	Day 1	Baseline Period (Days 3-16)		Treatment Period (Days 17-30)	
Procedure			Daily	Other	Daily	Other
Informed consent	X					
Review eligibility	X					
Physical examination	X					
Concomitant medication review	X	X				
Vital signs, weight	X	X 				
Serum creatinine, urine pregnancy test, ECG (12-lead)	X 					
Stool sample	X 			X 		
Anorectal study		X				
Randomization to treatment		X				
Study treatment administration		X				X 
Adverse event assessment		X		X 		X 
Stool diary (Appendix 1)			X		X	
Abdominal pain (Appendix 2)			X		X	
Global assessments (relief, severity) (Appendix 3)				Weekly		Weekly
Global assessment – satisfaction with treatment, (Appendix 4)	X			X (day 17)		X (day 31)
Other abdominal symptoms (Appendix 5)				Weekly		Weekly
Telephone contact				X  (q3-5 days)		X  (q3-5 days)

1. During the acute study, heart rate and blood pressure will be recorded at hourly intervals. Height (cm) and weight (kg) will be recorded at the screening visit but not on Day 1.
2. Urine pregnancy test to be performed for women of childbearing potential within 2 weeks of Day 1. Serum creatinine and ECG (12-lead) to have been done within three months of Day 1.
3. A single stool sample can be collected either before the acute study visit, or 3 days after the acute study visit, but before the treatment period.

4. Patients will be treated with placebo or alfuzosin ER (10 mg) once daily during this phase. While the protocol is planned for the treatment period to follow directly the baseline period, if needed for scheduling, there can be up to a 5-day interval between the baseline and treatment period.
5. Patients will be contacted by telephone every ~3-5 days between clinic visits to address questions, ascertain side effects and remind subjects to complete diaries. The final phone call will be within 5 days after completing the treatment period. Subjects will be asked to return unused medication by mail.

3. Experimental procedures. Items a-d below exclusively pertain to Part A,

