- a) Anorectal sensorimotor functions. After rectal cleansing with 1-2 sodium phosphate (Fleets®, C.B. Fleet, Lynchburg, VA) enemas, anorectal resting and squeeze pressures and rectal compliance and sensation will be evaluated before and after randomization to alfuzosin (2.5 mg oral) or placebo (Figure 1) in the Charlton 7 CRU. During each epoch (i.e., baseline or drug), pressures will be evaluated before and after patients are randomized to one of 6 sequences (orders) of 3 interventions (i.e., 2 stressors and active relaxation). The same stressor/relaxation sequence will be applied during pre-drug and post drug epochs. Anorectal assessments, which will be performed with standard techniques, include:
- Anal resting and squeeze pressures using high resolution manometry, similar to the procedure employed in the clinical lab and in recent studies;
  - Rectal compliance and sensation using a barostat/ polyethylene balloon. A conditioning distention from 0-40 mmHg in 4 mm steps at 15 second intervals will be performed. Ten minutes thereafter, the balloon will be distended from 0-44 mmHg or maximum tolerated pressure in 4 mmHg steps; sensory thresholds for first sensation, desire to defecate, and urgency will be recorded
  - Rectal ramp distention. Because the contractile response to distention is influenced by the rate of distention, a ramp distention to 200 mL over 1 minute will be performed; this will be sustained for 2 minutes. While (ii) is useful for characterizing quasi-static pressure-volume relationships representing colonic tone, ramp distentions can uncover the active contractile response to distention.
  - Rectal sinusoidal oscillation will be performed at 5 cpm for 20 minutes after distention to 125 mL. This paradigm is more sensitive than barostat-driven distentions for uncovering increased rectal stiffness in fecal incontinence but has not been evaluated in constipation

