Alfuzosin (2.5 mg) has a mean bioavailability of 64%,  $t_{max}$  of 1.0 – 1.5 hours and a terminal  $t_{half}$  of 3-5 hours. The drug is extensively metabolized by the liver with only 11% of the administered dose excreted unchanged in the urine. This immediate release formulation, which is also manufactured by Sanofi-Aventis, not approved in the US but widely available in other countries, will be imported from UK (Xatral™, 2.5 mg) under an investigator-initiated IND (117098) from the FDA because the long  $t_{max}$  for alfuzosin ER limits its use in this acute study.

f) Stool collection. Using stool kits and standardized instructions, patients will collect stool samples according to the procedure in the Appendix. Stool samples will be frozen and stored in a -20°C freezer. The first stool specimen will be collected (a) without a laxative in controls and (b) if necessary, after their usual laxative regimen in patients. In Part B, the effects of alfuzosin extended-release (10 mg, Uroxatral) on bowel

symptoms will be evaluated. Since such use satisfies the requirements of 21 CFR 312.2 (b) (1), an IND is not required. We confirm that all the following apply to Part B of this study:

a) The investigation is not intended to be reported to FDA as a well-controlled study in support of a new indication for use nor intended to be used to support any other significant change in the labeling for the drug; and

b) The investigation is not intended to support a significant change in the advertising for the product; and

c) The investigation does not involve a route of administration or dosage level or use in a patient population or other factor that significantly increases the risks (or decreases the acceptability of the risks) associated with the use of the drug product; and

d) The investigation will be conducted in compliance with the requirements for institutional review set forth in 21 CFR 56 Institutional Review Boards and with the requirements for informed consent set forth in part 21 CFR 50 Protection of Human Subjects; and

e) The investigation will be conducted in compliance with the requirements of 21 CFR 312.7 - Promotion of Investigational Drugs.

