g) **Sequencing and analytical methods.** Using resources available in the UIUC-Mayo consortium, two complementary approaches will be utilized to analyze stool specimens from each subject. First, microbial DNA will be extracted from stool and tissue samples using standardized methods [33]. Phylotype profiles of the microbiome from control and constipated populations will be generated using deep rDNA hypervariable tag sequencing of the hypervariable V3-V5 region of the SSU rRNA gene, which has been validated for use with human microbiomes and is one of the methods of choice for the HMP. With the longer reads from the MiSeq (250x250 paired end reads), our sequencing will include both the V3-V5 RGTs making for a more optimal phylogenetic analysis [34]. Phylotype profiles of the mucosa-associated microbiome will be generated using rDNA sequencing of the hypervariable V3-V5 region, which has been validated for standard use by the human microbiome project. The 300 base pair reads will ensure a better optimal phylogenetic identification. Barcoding samples prior to sequencing will yield approximately 20,000 reads/sample, ensuring detection of both dominant (core microbiome) and poorly represented taxa (variable microbiome). Identifying the existent taxa, diversity, and ecological relationships within each sample requires that we process large volumes of 16S DNA sequence data. In order to accomplish this task we will follow protocols that we have quantitatively shown to be optimal. Paired end reads will be stitched, aligned, and classified using a custom pipeline (TORNADO v2.0).[35] Briefly, low base quality reads will be either trimmed or discarded,[36] and these reads will not be classified as a bacteria kingdom[37] or matched to the bacteria 16S rRNA secondary structure.[38] To evaluate the microbial diversity and abundance, UPARSE will be used for Operational Taxonomical Units (OTU) clustering,[39] and FastTree for phylogeny.[40] The 16S data will be clustered into OTUs at 97% sequence similarity, and the taxonomy will be assigned using the Ribosomal Database Project classifier. h) Effects of alfuzosin in bowel habits (Part B). During the first 2 weeks, bowel habits will be recorded at baseline. During the next 2 weeks, patients will be treated (double-blind) with placebo or alfuzosin (10 mg) ER once daily, which is FDA-approved dose for urinary symptoms. Symptom assessments are shown in Table 1 and in Appendices 1-5. Per eligibility criteria, subjects will discontinue medications which can affect GI transit during the baseline and treatment periods. Patients who need rescue medication, after three full days without a bowel movement, can receive 1-2 bisacodyl 5 mg tabs or a bisacodyl suppository (10 mg) or up to Fleet's enemas. In addition, patients who need relief of mild pain can use analgesic drugs such as NSAIDs and COX-2 inhibitors for up to two doses per week. During the procedure, intake of acetaminophen up to 1.5g per day in divided doses will be permissible.

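### Stool may follow a laxative in patients but not in controls, and the plan neither ties that exposure to the sample nor uses it in a microbiota analysis

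*Combined protocol and SAP*

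**What the plan says.** **Laxatives.** Section B.3, under Stool collection: "The first stool specimen will be collected (a) without a laxative in controls and (b) if necessary, after their usual laxative regimen in patients".

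**Timing.** Table 1, note 3: "A single stool sample can be collected either before the acute study visit, or 3 days after the acute study visit", provided that it precedes the treatment period. The note does not limit either option to one group.

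**Bowel preparation.** The acute visit (Section B.3.a) opens with enemas: "After rectal cleansing with 1-2 sodium phosphate". Study drug or placebo and the stress and relaxation tasks take place at the same visit. Part A, which includes this visit, covers controls and patients.

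**Intended comparison.** Section A: "It is thus important to also evaluate the gut microbial profile in patients and controls". Section B.3, Sequencing and analytical methods: "Phylotype profiles of the microbiome from control and constipated populations will be generated". The hypothesis stated under Aim 6 concerns susceptibility to stress and fecal microbiota.

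**Laxative withdrawal.** Exclusion criterion v in Section B.1.c applies to patients as well. It excludes those who cannot stop laxatives before the baseline period and during the study, apart from protocol-defined rescue. Section B.3.h adds: "subjects will discontinue medications which can affect GI transit during the baseline and treatment periods".

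**Analysis.** Section B.4 covers manometry, rectal function, bowel symptoms and adverse events. It has no microbiota analysis. The sequencing section describes how reads are processed and clustered, but no group test, covariate, restriction or sensitivity analysis.

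**The concern.** A laxative before sampling is ruled out in one group and allowed in the other. If laxatives shift the microbial profile, part of any patient-control difference would be a laxative effect, and the plan has no step that would show how much. The information may also be lost: if the last laxative is not noted when the stool is collected, it may not be recoverable later.

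The two sampling times are a separate and weaker matter. A later sample follows the Day 1 enemas, a dose of drug or placebo, and the stress tasks, whereas an earlier one does not. Mixing the two adds variability to every microbiota comparison, including the stress association in Aim 6.

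**Working it through.** The documents give no sample size, power, test or effect size for the microbiota aim, so there is no stated figure to reproduce. The main check is textual.

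**1. Is exposure tied to group?** Yes. Controls have none by rule. In patients the share exposed can be anything from 0 to 100%, because a laxative is allowed only where needed.

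**2. Would existing records identify exposed samples?** Only in part.
- Concomitant medication is reviewed at screening and Day 1 (Table 1), with no stated link to the stool sample.
- The daily diary is kept in Part B, which controls do not enter. Its medication question (Appendix 1) leaves out drugs that the patient uses routinely, so a usual laxative could go unrecorded.
- The diary would pick up rescue use, and it has a code for a stool that needed an enema. The definition of a spontaneous bowel movement in Section B.4.b also depends on laxative, enema or suppository use in the preceding 24 hours. None of this is linked to the sample.

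**3. Can group and laxative be separated in principle?** Take mean = a + b × group + c × laxative, with laxative = 0 in every control. Controls have mean a, unexposed patients a + b, and exposed patients a + b + c. So b is exactly unexposed patients minus controls. In this model adjustment amounts to restriction. It works if some patients are unexposed and fails only if all are exposed. Either way, exposure must be known for each sample.

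**4. Is either sampling time clean?** Neither is fully clean for patients.
- Before the acute visit: no Day 1 enemas, but the usual laxative may apply.
- After the visit, in the baseline period: transit-altering drugs are stopped, but the sample follows the enemas and may follow rescue, which is provided for in Part B patients only.

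For controls, who have no treatment period, note 3 sets no end date for the later option.

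**5. Illustrative size.** The share exposed and the effect in SD units are assumptions. With 36 per group (Section B), a within-group SD of 1, no true disease effect and a two-sided 5% test:
- false difference δ = (share exposed in patients − share exposed in controls) × effect;
- SE = √(2/36) = 0.236;
- rejection probability = Φ(δ/SE − 1.96) + Φ(−δ/SE − 1.96).

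| Patients exposed | δ at 0.5 SD | Rejects | δ at 1.0 SD | Rejects |
|---|---|---|---|---|
| 25% | 0.125 | 8% | 0.25 | 19% |
| 50% | 0.25 | 19% | 0.50 | 56% |
| 75% | 0.375 | 36% | 0.75 | 89% |

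This ignores the extra spread from mixing exposed and unexposed patients. At 50% and 1.0 SD the patient variance would be 1 + 0.5 × 0.5 × 1 = 1.25 and SE = √(2.25/36) = 0.25, so the 56% becomes Φ(0.50/0.25 − 1.96) = Φ(0.04) = 52%.

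For enema timing the same formula gives zero bias and 5% rejection when both groups have the same share of later samples. Shares of 75% and 25% would give a false difference of 0.25 to 0.50 SD and 19% to 56% rejection.

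**6. Cost of restriction.** By a two-sample t-test with 80% power, 36 against 36 detects 0.67 SD. With 27, 18 or 9 laxative-free patients against 36 controls, the figures are 0.72, 0.82 and 1.07 SD.

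**The case against.** The strongest reply has four parts.

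- **Separable.** A reader might infer that disease and laxative effects cannot be separated at all. The documents do not support that. Patients take a laxative only where needed, so some may be unexposed, and step 3 shows that the contrast can then be estimated. This stands: the effects are not separated under the plan, which is different from being inseparable.
- **Enemas.** A reader might also infer that the enemas confound the group comparison by design. Both groups have them, both have the same timing options, and the later option is 3 days after the visit. With the stated half-life of 3 to 5 hours for the 2.5 mg dose, 72 hours is at least 72/5 = 14 half-lives, so residual drug is not the issue. This stands: timing is noise unless it differs by group. Nothing balances it, however.
- **Target.** Aim 6 is framed around stress susceptibility, and no between-group microbiota test is stated. This stands in part. The group contrast is only part of the aim, but profiling both groups is explicitly intended.
- **Size.** The documents do not say that laxatives, or enemas three days earlier, alter these profiles. This stands, and the figures in step 5 show only what would follow if they did.

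The reply that exposure is already recorded stands only for rescue use in patients during Part B. It does not cover routine laxatives at the time of sampling.

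**Conclusion.** The concern holds in this form. The collection rule allows laxative exposure in patients only, the exposure is not tied to the sample, and no analysis uses it. As the plan stands, a patient-control microbiota difference could not be attributed to disease rather than to laxatives. The sampling-time option adds variability and biases the contrast only if the groups differ in when they sample.

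The size cannot be derived from the documents. The table above rests on assumed exposure shares of 25% to 75% and assumed effects of 0.5 to 1.0 SD. The point is minor for the trial as a whole, since it touches one of six aims and leaves the manometry and bowel-symptom analyses unaffected. It is worth acting on because the remedy is cheap and exposure may not be recoverable after collection.

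Two textual conflicts remain. The usual laxative regimen in the stool section sits against laxative withdrawal in exclusion criterion v and Section B.3.h. The stool section's reference to a first specimen sits against the single sample in Table 1, note 3.

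**What to change.** 1. Record with each sample, in both groups, the collection date, the date of the last laxative, rescue medication or enema, and whether the sample came before or after the acute visit.
2. Add a microbiota analysis to Section B.4, with sampling time relative to the acute visit as a covariate.
3. Prespecify a sensitivity analysis comparing laxative-free patient samples with controls. State that this set is smaller and may contain less severely affected patients, so it reduces confounding at the risk of selection. For that reason it serves better as a sensitivity analysis than as the main comparison.
4. Reconcile the passages on laxative use around sampling and on the number of specimens. Which rule applies is for the investigators to decide.

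The cost is a few entries on the collection form and a short paragraph in the analysis section. Patient care need not change. The statistical cost is the loss of precision in step 6: for example, 0.82 SD detectable instead of 0.67 SD if half the patients are laxative-free.

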
#### 4. Data and statistical analysis

a) Part A. Anal manometry will be analyzed by established techniques and summarized as anal resting and squeeze pressures, rectal and anal pressure and rectoanal gradient during evacuation. Rectal pressure-volume relationships will be summarized by the  $P_{r_{half}}$  during rectal compliance, rectal capacity, pressure and volume sensory thresholds for first sensation, desire to defecate, and urgency. During

sinusoidal oscillation, average rectal pressures and the variability in pressures over 20 min will be summarized.

The analysis will be based on analysis of covariance (ANCOVA) models to assess the pre-dug period for intervention effects with subject status and intervention type as the primary factors (a check for order effects of the intervention sequences will also be made, and the corresponding pre-stress response will be included as a covariate). Models with a subject status by intervention type interaction will also be examined. During period 2, subjects will have been randomized to drug or placebo (balanced on subject status) and use the same intervention sequence as the pre-drug period). The analysis of the post drug period will also be based on ANCOVA models incorporating subject status, intervention type, treatment group, and corresponding interactions (a check for order effects will again be made). The corresponding responses from the pre-stress interval from period 1 and VAS scores for stress and arousal will be used as covariates,

b) Part B.

- i. Endpoints. Symptoms and Signs of Chronic Constipation. The effects of alfuzosin compared to placebo will be assessed by evaluating
  - Bowel habits using a daily diary (Appendix 1) to record stool consistency (Bristol Stool Form scale), frequency, ease-of-passage and sensation of complete bowel emptying (yes/no)
  - Daily Abdominal Pain Scores (Appendix 2) collected as (a) most severe daily score and (b) overall average daily score).
  - Global Patient Treatment Assessments reporting outcomes on a weekly basis (Appendix 3) including overall relief and severity of constipation
  - Global Patient reported outcomes on a 2-week basis (Appendix 5)
  - Patient reported outcomes of other abdominal symptoms (Appendix 6)

Two outcomes will be derived from primary data.

  - Weekly rate of SBMs: a bowel movement (BM) is considered an SBM if no laxative, enema or suppository was taken in the preceding 24 hours.
  - Weekly rate of CSBMs: if the patient indicated that the SBM was associated with a sensation of complete bowel emptying, the SBM will be counted as a CSBM.
- ii. Analysis. Daily bowel diary responses will first be averaged over study periods (baseline and treatment) and in the case of stool frequency, per week. These responses will also be assessed using ANCOVA models, with the corresponding baseline value as the primary covariate. For stool frequency, the two weekly values will be assessed using a repeated measures ANCOVA model with the overall average baseline stool frequency value as a covariate. The global assessment scores (adequate relief and severity) will first be summed over the two treatment weeks, and then assessed using the Wilcoxon rank sum test. Individual adverse events (AEs) will be summarized by treatment group and the overall total frequency (per subject) of AEs assessed using the Wilcoxon rank sum test. The analyses will follow the intent to treat (ITT) paradigm with all

- patients randomized included in the analyses. Patients with missing values for a particular endpoint will have their missing values imputed using the corresponding overall mean value from all patients with non-missing data for that endpoint. An adjustment in the ANCOVA error degrees of freedom (subtracting one for each imputed value) will be made to account for the imputation. A similar adjustment for the Wilcoxon rank sum test (adjusting the degrees of freedom for the t-approximation) will also be examined.
5. Sample size assessment. The sample size assessment is based on the variation in anal resting pressures in healthy subjects and patients with defecatory disorders and the effect of the  $\alpha_1$  receptor antagonist (indoramin) on anal resting pressure in a previous study. The CV (%) in anal resting pressure evaluated by the same technique in healthy women (<50 years old) and patients with defecatory disorders (<50 years old and resting pressures >90) was 20% (mean=93.7{SD=18.5}) and 11% (mean=102.9{SD=11.7}), respectively. In period 2 the sample size of 36 controls and 36 patients will yield 18 subjects per treatment arm (drug vs. placebo) in each subject group (control vs. patients). This should provide 80% power to detect a treatment effect size of roughly 15-20%, based on a two sample t-test with a two-sided alpha level of 0.05 separately in each subject group. The effect size is defined as the difference in group means as a percentage of the overall (both groups) mean value. The previous study suggested an effect size of 47% for drug effects. For part B, data pooled from constipation subjects imply differences between treatment groups of ~4 stools per week, differences in stool consistency scores of ~1.1 and differences in ease of passage scores of 0.8 could be detected with 80% power (2-sided alpha level of 0.05). It is anticipated that the ANCOVA models will provide similar power for somewhat smaller differences by incorporating the baseline values as covariates.
  6. Anticipated results and interpretation. We anticipate that: (i) alfuzosin will reduce anal resting pressure and increase the rectoanal gradient during simulated evacuation but not affect the squeeze increment; (ii) alfuzosin will attenuate the augmentation of anal pressure by mental stress; (iii) mental relaxation will reduce anal resting pressure to a greater extent after placebo than alfuzosin; and (iv) rectal compliance and the contractile response to sinusoidal oscillation will be lower in chronic constipation than in healthy subjects.
  7. Potential pitfalls and precautions taken. The anorectal procedures to be used in this study are established in our laboratory. While the effects of alfuzosin on anal pressures are unknown, the dose used in this study is safe and relaxes the urethral sphincter to increase urinary flow. Peripheral arterial tonometry will provide an independent biological marker for effects of stress and alfuzosin. We recognize the given the phenotypic variability in defecatory disorders, it is conceivable that only a subset of patients will respond to an  $\alpha_1$  antagonist. To maximize the likelihood of a response, patients with high anal resting pressure by digital rectal examination or manometry will be recruited for initial studies. Established perturbations administered in a standardized format will be used to modulate arousal and anxiety and the effects of these

perturbations will be evaluated by standardized and validated VAS instruments. While the sample size estimate is primarily designed to detect acute effects on anorectal functions, it is also sufficient to identify clinically-significant effects on bowel symptoms (eg, bowel symptoms).

8. Innovative aspects, significance, and future directions. The concepts that mental stress can increase anal resting pressure via  $\alpha$ -1 adrenergic receptors and the application of  $\alpha$ -1 antagonists to manage these disorders are novel. Alternative approaches to pelvic floor retraining, which is the cornerstone for managing defecatory disorders, are necessary because (i) many insurance programs do not cover pelvic floor retraining; and (ii) our experience suggests that a considerable proportion of patients do not respond to pelvic floor retraining in clinical practice. If alfuzosin reduces anal resting pressures and increases the rectoanal gradient during defecation, further studies with the long-acting formulation, either alone or as an adjunct to biofeedback therapy, will be considered. Likewise, further studies to evaluate the effects of mental relaxation on symptoms and to understand the extent to which the effects of biofeedback therapy are mediated by mental relaxation in patients with DD may be considered. Conceivably, the response to these approaches may vary among patients and the acute response to these perturbations may predict response to chronic therapy.

